3.1 General Design

We propose a phase III comparative effectiveness study to evaluate the added value of an attending nurse to the inpatient care of stroke patients compared to routine care. Both types of care are currently available on the inpatient Vascular Neurology service at the Hospital of the University of Pennsylvania as well as at other institutions. Currently, the nurse attending works randomly with patient she selects based on her availability.

In the standard model of inpatient nursing care, stroke education is provided largely in the form of pamphlets distributed to patients and their families. Patients are cared for by a team of physicians and staff nurses with access to social workers and case managers, however, staff nurses do not routinely round on their patients with other members of the care team.

Screening of patients for this trial will occur once the clinical decision to admit a patient to the Vascular Neurology service has been made. All patients who meet inclusion criteria will be assigned to a study arm, addition of an attending nurse versus routine nursing care, according to the day of the week they are admitted to the hospital. Patients who are admitted on even numbered week days will have their care supplemented by the attending nurse. This is effectively a stratified random assignment, as there are no clinical or systematic features that otherwise are associated with odd or even numbered days. The duration of the intervention will depend on the duration of a patient's hospital admission.

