3.1.3 Allocation to Interventional Group

Stroke patients who are admitted on even-numbered weekdays and enrolled in this trial will be assigned to care with an attending nurse; patients admitted on odd-numbered weekdays will get usual routine care. The attending nurse will query the electronic medical record as well as communicate with the physician team so that all incoming admissions on even-numbered days to the Vascular Neurology service are known to the attending nurse.

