5.2 Intervention Regimen

The attending nurse will spend 30 minutes to 45 minutes upon initial evaluation to determine the patients' goals, barriers, and needs. The amount of time spent with each subject following the initial visit will vary based on the patient. To limit the demands on the attending nurse, she will never carry a case load of more than 8 patients at a single time. If on an even-numbered weekday the attending nurse has 8 patients, than the subject will be assigned to the routine care arm of the trial. Patients who are assigned to the attending nurse model of care will be seen by that nurse on a daily (weekday) basis in addition to being cared for by their regular care team of physicians and rotating staff nurses. All staff nurses as well

as the attending nurse will participate in morning interdisciplinary table rounds in keeping with preexistent quality processes.

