6.2 Study Intervention Phase

If patients satisfy inclusion criteria and lack exclusion criteria they will be assigned to the intervention arm or the control arm depending on their admission date. The intervention phase will be the duration of the patient's hospital stay.

No research related procedures that differ from standard of care will be conducted as this is a comparative effectiveness trial.

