7.3 Sample Size and Power Determination

For this pilot project, we anticipate that 65% of patients in the control arm will be adherent to medications (MMAS-4 < 2) based on literature reporting 60%¹⁶ adherence as evaluated using these scales in stroke patients and 70%²¹ adherence in patients with hypertension. To achieve success on the primary endpoint, we estimate that patients must improve to by 15% in order to make this intervention worthy of future investigation in a larger study. Assuming an alpha of 0.05 and a power of 80%, with a 1:1 assignment to each arm, we will require 186 patients in each arm for a total of 372 patients. With that number of patients

we will be able to powered to detect a very small difference of 0.3 (delta = .15 (SD=2)) in the mean scores of the SPER based on the published data.¹⁷ Each outcome will be evaluated independently so that we will not need to make any power readjustments. Readmission rates at 30 days are typically low⁴ and likely lower at our institution based on prior data so we will be underpowered for this outcome. Clinically differences on the SIS will depend on the initial stroke severity of patients within each group and therefore the study cannot be powered for this secondary endpoint.

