7.4 Statistical Methods

In our primary analysis, we will first compare baseline demographics between groups. For our results section, we will compare all patients in the control group to all patients in the intervention arm for outcomes. Mean scores on the SPER will be compared between groups using student t-tests. We will compare proportions of adherent patients on the MMSA-4 between groups using the Pearson chi-square test. Total scores on the SIS, quality of life questions, and the 13 newly devised questions will be compared between groups using t-tests.

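### Arm is set mainly by admission day, but the primary tests treat patients as independently assigned; the likely effect is modest and cheap to handle once the allocation wording is reconciled

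*Combined protocol and SAP*

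**What the plan says.** Three sections describe the allocation, each in different terms.

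- Section 3.1.3: "Stroke patients who are admitted on even-numbered weekdays and enrolled in this trial will be assigned to care with an attending nurse". Odd-numbered weekdays go to routine care.
- Section 3.1: patients are allocated "according to the day of the week they are admitted to the hospital". It then adds: "This is effectively a stratified random assignment".
- Section 6.2: patients are "assigned to the intervention arm or the control arm depending on their admission date".

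Section 5.2 makes one exception. If, on an even-numbered weekday, "the attending nurse has 8 patients, than the subject will be assigned to the routine care arm of the trial".

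The analysis in section 7.4 is at patient level. For the first primary endpoint: "Mean scores on the SPER will be compared between groups using student t-tests". For the other: "We will compare proportions of adherent patients on the MMSA-4 between groups using the Pearson chi-square test". The sample size in section 7.3 rests on: "Assuming an alpha of 0.05 and a power of 80%, with a 1:1 assignment to each arm". It arrives at 186 patients per arm, 372 in all. Sections 7.3, 7.4 and 7.5 contain no design effect, within-day correlation, clustered standard error or term for admission day.

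**The concern.** Apart from the caseload exception, patients admitted on the same day go to the same arm together, so the day rather than the patient is the main unit of assignment. If same-day patients resemble each other in outcome, the arm means vary more than a patient-level t-test or chi-square test allows.

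Some resemblance is plausible. The attending nurse is to meet each patient within 24 hours (section 5.1) and spend 30 to 45 minutes on the first evaluation (section 5.2), so intervention patients admitted on one day draw on the same person's time. SPER measures retained education, which depends on that time. At stake are the standard errors, p-values and nominal 5% level for both primary endpoints. Section 7.3 evaluates each outcome on its own without adjustment, so nothing else in the plan offsets extra error.

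**Working it through.** **The plan's own figure.** For 65% versus 80%, two-sided alpha 0.05 and 80% power, the usual two-proportion formula gives

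n = [1.96·√(2·0.725·0.275) + 0.84·√(0.65·0.35 + 0.80·0.20)]² / 0.15² ≈ 138 per arm.

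This is not the stated 186. At 186 per arm the power is 90.3%. That mismatch is a separate matter. It is relevant here only because it makes the unadjusted power about 90% rather than 80%.

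**Patients per day.** Section 4.5 gives about 7 months of recruitment.

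- Calendar days: 365 × 7/12 ≈ 213, and 372/213 ≈ 1.75 per day.
- Weekdays only: (365/7) × 5 × 7/12 ≈ 152, and 372/152 ≈ 2.45 per day.

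The second figure is an upper end. Section 4.5's 700 to 800 admissions a year, spread evenly over the week, yield about 700 × 7/12 × 5/7 ≈ 292 to 800 × 7/12 × 5/7 ≈ 333 weekday admissions in 7 months, which is fewer than 372.

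**Formulas.** With Poisson-varying numbers per day (mean m) and day effects independent from one day to the next:

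- design effect DE = 1 + m × ICC
- type I error of the unadjusted test = 2 × [1 − Φ(1.96/√DE)]
- effective patients per arm = 186/DE

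The ICC values are assumptions. The simulated column is the t-test over alternating days, 8,000 runs per setting.

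| ICC | m | DE | Type I, formula | Type I, simulated | Effective n per arm | Power, 65% v 80% |
|---|---|---|---|---|---|---|
| 0.01 | 1.75 | 1.017 | 5.2% | 5.2% | 183 | 89.8% |
| 0.01 | 2.45 | 1.024 | 5.3% | 5.1% | 182 | 89.6% |
| 0.05 | 1.75 | 1.087 | 6.0% | 5.9% | 171 | 87.8% |
| 0.05 | 2.45 | 1.122 | 6.4% | 6.7% | 166 | 86.7% |
| 0.10 | 1.75 | 1.175 | 7.0% | 7.3% | 158 | 85.2% |
| 0.10 | 2.45 | 1.245 | 7.9% | 8.0% | 149 | 83.1% |

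At an ICC of zero the simulated error is 4.9%, so nothing changes. With independent day effects, date-clustered standard errors held the simulated error at 5.0 to 5.4% across these ICC values (20,000 runs).

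**Day effects that persist.** Alternating days balance slow-moving effects between arms. With 152 alternating days, 2.45 patients per day and an assumed day-to-day autocorrelation of 0, 0.5 and 0.7, the t-test's error was 6.3%, 5.6% and 5.3% at ICC 0.05, and 7.9%, 6.2% and 5.6% at ICC 0.10. At autocorrelations of 0.5 to 0.9, date-clustered errors were mildly conservative: 4.1 to 4.4% at ICC 0.05 and 3.3 to 3.8% at ICC 0.10. Simulation error is about a quarter of a percentage point (√(0.055 × 0.945/8,000) ≈ 0.0025).

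**Literal day of the week.** Five weekdays would be five clusters of 372/5 = 74.4 patients. With equal sizes, DE = 1 + 73.4 × ICC. That is 1.73 at ICC 0.01 (type I error about 14%) and 4.67 at ICC 0.05 (about 36%).

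**The case against.** The strongest reply has four parts.

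- **Whole days are not assigned without exception.** Under the caseload limit in section 5.2, an even-numbered day can supply patients to both arms. This stands. The day is the main basis of assignment but not the only one. Date clustering still works when a day contains both arms.
- **The within-day mechanism is inferred.** Staff nurses rotate, the attending nurse follows patients to discharge and so serves several admission days at once, and the primary outcomes are telephone answers at 7 and 90 days. Nothing in the documents supports an ICC as high as 0.05 or 0.10. This stands too, and it is why the result is given as a range. Refusals and missed calls would shrink the analysed clusters further.
- **Positive correlation need not inflate the error.** A reader might infer that any within-day correlation makes the p-values too small. With alternating days that is not so: if day effects carry over to the next day, most of the excess disappears.
- **The consequence is small.** Even at ICC 0.10 the MMAS-4 power stays above the planned 80%, and section 7.3 calls the study a pilot project. That limits the weight of the point. It does not remove the mismatch between how arms are assigned and how uncertainty is computed, which costs almost nothing to correct.

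**Conclusion.** The point holds in a limited form. Arm depends mainly on admission day, the planned tests assume independently assigned patients, and no part of the statistical plan accounts for the day. On the calendar-date reading, with 1.75 to 2.45 patients per day and independent day effects, the standard error is understated by about 1% at ICC 0.01 (√1.017 to √1.024) and 4 to 6% at ICC 0.05 (√1.087 to √1.122). Type I error lies between about 5% and 8% over ICC 0.01 to 0.10, and MMAS-4 power between about 83% and 90%, taking the 15% improvement as absolute. With persistent day effects the inflation is mostly gone.

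A reader might go further and infer that the trial has only five clusters and an error rate of 14% or more. The documents do not establish that. Section 3.1 does speak of the day of the week, but the same section reasons about odd and even numbered days, and section 6.2 refers to the admission date. The wording is unresolved, and it matters: under a literal day-of-week rule, arm would be confounded with weekday.

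**What to change.** 1. Reconcile sections 3.1, 3.1.3 and 6.2 so that they state one rule: calendar date or day of the week, and how weekend admissions are handled. The remaining steps apply to the calendar-date reading; they would not rescue a literal day-of-week assignment.
2. In section 7.4, keep the same contrasts but estimate them by regression on arm: linear for the SPER mean difference, and binomial for the MMAS-4 risk difference. Cluster standard errors by admission date, or use GEE with date as the cluster, and report 95% confidence intervals.
3. In section 7.3, add one line stating the assumed within-day correlation and design effect.

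The cost is small. Section 9.2 already has the dates of hospital stay abstracted and names STATA or SPSS for the analysis. The downside is slightly wider intervals, which may be mildly conservative if day effects persist across adjacent days.

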7.4.1 Baseline Data

Baseline and demographic characteristics will be summarized by standard descriptive statistics (including mean and standard deviation for continuous variables such as age and standard percentages for categorical variables such as gender). Stroke severity and PMH will also be collected and compared between the groups.

7.4.2 Efficacy Analysis

Our efficacy endpoint is the same as our primary endpoints as this is a comparative effectiveness study.

7.4.3 Safety Analysis

Given that we are comparing two models of nursing care, safety of subjects will be tracked via the general quality controls already in place for inpatient safety. There are no unique safety outcomes for this trial.

7.5 Subject Population(s) for Analysis

The entire subject population who undergo treatment assignment will be studied primarily via intention to treat analysis comparing data from follow up phone calls between groups. An as-treated analysis will also be performed.

Analysis will be performed on some pre-defined subgroups where we may expect to see effect modification: major stroke vs. minor strokes (NIHSS \leq 5), multiple medications vs. few medications, patients who were admitted following a recurrent stroke vs. a new stroke, and hemorrhagic stroke vs. ischemic stroke subtypes.

8 Safety and Adverse Events

This protocol is extremely low risk as it assigns patients to already existent forms of inpatient care. This study does not include any experimental treatment. Given there is no proposed intervention or proposed management beyond two existing forms of standard clinical care, the routine collection of adverse events is not relevant, as those will be part of routine care. However, there may be a difference between the two arms in terms of specific events of interest. These specific events of interest include falls, aspiration pneumonia, and subsequent (post-discharge) major cardiovascular and cerebrovascular events (MACCE) including stroke (ischemic, hemorrhagic, or unknown), myocardial infarction, and death of any cause. Transfers to a higher level of care (e.g. to the Neuro ICU or medical ICU from the floor) that occur as part of routine care will also be considered events of interest. We will also report any unanticipated events.

All of the aforementioned events of particular interest will be assessed while the subject is in the hospital in keeping with standard clinical care. During follow up phone calls, the interviewee will ask patients and/or their family members specifically about the occurrence of MACCEs including and death of any cause.

The safety of each mode of nursing care while the subject is in-house will be tracked using the quality control processes that are already in place as part of standard inpatient care.

9 Study Administration, Data Handling and Record Keeping

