To compare the two models of nursing care, we will survey all patients directly about the care they receive in the hospital once they are discharged. Surveys tools designed to ascertain medication adherence, disease specific knowledge, as well as satisfaction with care and hospital readmissions will be assessed at 7, 30, and 90 days via follow-up structured telephone interviews. We will consider the 7 day follow-up phone call the baseline assessment. The Morisky scale (MMAS-4),¹⁵ a well validated tool that has been studied in stroke victims,¹⁶ will be used to determine medication adherence. The Stroke Patient Education Retention (SPER)¹⁷ tool will be used to assess patient knowledge. The Stroke Impact Scale (SIS)¹⁸ will be used to evaluate self-perception of stroke deficits by patients. Thirteen other survey questions designed specifically for this study will also be posed to patients at 7, 30 and 90 days from follow up along with two overall quality of life questions at 7 and 90 days. As a secondary outcome, we will calculate and then use a global statistic as a general marker for success to compare the effectiveness of each nursing care model in improving patients' overall outcomes.¹⁹ All interviews will be performed by a trained research assistant who will not be involved in the inpatient care of patients and will be blinded to study allocation. Subject participation will conclude after 90 days.

We will request a waiver of consent for initial enrollment in this study. Follow-up calls to patients will explicitly state according to an IRB-approved script that the questions are part of a research study. Patients will also be asked if they consent to collection of data from their medical record as part of the study. Patients will have the option to participate or decline. If they choose to participate in the interview survey and allow collection of data from their recent hospitalization, then the study will proceed with their verbal consent.

If they decline to participate in the interview survey, then no further study specific tools will be used, but they will be asked if they consent to chart abstraction. However, patients cannot participate in interviews without agreeing to data collection. Patients can decline to participate in both the interviews and allow for data collection. If they fully decline to participate in the study, their data will be expunged and no further data collected.

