5.5 Subject Compliance Monitoring

Patients will be called at 7, 30, and 90 days following discharge to evaluate their response to the questionnaires. Incomplete response at 7 days will not preclude a phone call directed to patients at 30 and 90 days. Patients who are not reachable via phone interview will not undergo an analysis of their clinical data due to lack of consent.

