Patients may withdraw from the study at any time without impact to their care. Patients may also be discontinued from the study at the discretion of the PIs for lack of adherence to intervention or study procedures or difficulty obtaining follow up or unexpected events. The PI may also withdraw patients who violate the study plan, or to protect the subject for reasons of safety or for administrative reasons. It will be documented whether or not each subject completes the study.

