6.5.1 Data Collection and Follow-up for Withdrawn Patients

If patients decide to stop participating in inpatient care when recommended by the treating team, documentation for patient decisions against medical advice (AMA), this will be documented in keeping with standard practice. Follow up phone calls will still be sought on patients who leave AMA. Patients who are lost to follow up or decline to participate in follow up phone calls and do not consent to data abstraction from the inpatient record will not have any further data collected.

Patients who request to be removed from the study will have all available data expunged.

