11.4 Informed Consent Process / HIPAA Authorization

A waiver of consent will be obtained for the initial intervention as detailed below. We will obtain informed consent using a verbal process, detailed below, for data abstraction from the medical record as well as follow up phone questionnaires at the 7 day phone call. We will thus request a waiver of written consent.

Consent will be obtained by the interviewer administering the questionnaires to the patient following verbatim a script approved by the IRB. Consent for all follow up phone surveys as well as chart abstraction from the inpatient stay will be obtained at the 7 day phone call. The consent process will take place over the phone. Subject privacy will be assured as all data will be stored securely and interviews will be conducted in private space.

Patients will be permitted to provide consent at the time of the consent discussion over the phone (e.g. verbal consent) given the low risks associated with this study. Patients can ask the interviewer to call back at a later time to avoid any coercion associated with time pressures. The subject will be informed that they can withdraw their consent at any point. Investigators will confirm that the patient understands the study by asking them if they have any questions or need any points clarified in keeping with the phone call transcript.

Documentation of informed consent (e.g. date and time, who obtained consent, who gave consent and subject ID number) will be made by the interviewer on the case report form as consent will be verbal. If the subject is unable to provide consent, their legally authorized representative may.

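### Section 7.5 promises intention to treat on everyone assigned, but both primary endpoints exist only for patients reached and consenting after treatment, and no planned analysis addresses selective response

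*Combined protocol and SAP*

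**What the plan says.** Section 7.5 defines the primary population: "The entire subject population who undergo treatment assignment will be studied primarily via intention to treat analysis comparing data from follow up phone calls". It adds one other analysis set: "An as-treated analysis will also be performed".

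Other sections decide who can supply those data:

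- **Timing of consent (11.4).** "Consent for all follow up phone surveys as well as chart abstraction from the inpatient stay will be obtained at the 7 day phone call". Assignment happens at admission and the intervention ends at discharge, so consent follows the whole intervention.
- **Unreachable patients (5.5).** "Patients who are not reachable via phone interview will not undergo an analysis of their clinical data due to lack of consent".
- **Interview decliners (3.1).** For them, "no further study specific tools will be used, but they will be asked if they consent to chart abstraction".
- **Full decliners (3.1).** For them, "their data will be expunged and no further data collected".
- **Removal on request (6.5.1).** "Patients who request to be removed from the study will have all available data expunged".
- **Discontinuation by the investigators (6.5).** Permitted reasons include "lack of adherence to intervention or study procedures or difficulty obtaining follow up or unexpected events".

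Section 7.4 specifies t-tests for SPER and a Pearson chi-square test for MMAS-4 adherence. The protocol states no expected response rate, imputation, weighting, missing-data sensitivity analysis or comparison of response between arms.

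**The concern.** An intention-to-treat comparison keeps the balance created at assignment because nobody leaves for reasons that arise afterwards. Here, entry to the analysis depends on two events after treatment: being reached by telephone and agreeing to take part.

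The documents give reasons why these could differ by arm. Section 1.1 describes the intervention as building a therapeutic relationship. Section 5.3 says patients are not formally blinded. Section 11.4.1.1 has callers tell patients, before they decide, that they received one of two nursing models under comparison. The same section accepts that knowing one's arm may colour expectations and satisfaction.

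If response differs by arm and is related to adherence or stroke knowledge, the comparison can show an effect that is not there or hide one that is. The report would carry a label implying that this cannot happen.

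**Working it through.** **Inputs from the protocol.** Control adherence 65%, a 15-point improvement (read as absolute), 186 per arm, alpha 0.05 (taken as two-sided), power 80%, and a SPER difference of 0.3 (all 7.3); SPER maximum 10, minimum 0 (7.1). **Not in the protocol:** response rates and adherence among non-responders. Values used for these are assumptions.

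**Step 1. Who can contribute a primary outcome**

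| Assigned patient | Section | SPER and MMAS-4? |
|---|---|---|
| Reached, agrees to interview | 11.4 | Yes |
| Declines interview, allows chart review | 3.1 | No |
| Declines both | 3.1 | No, data expunged |
| Not reached | 5.5 | No |
| Asks to be removed | 6.5.1 | No, data expunged |
| Discontinued by the investigators | 6.5 | None after discontinuation |

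Only the first row supplies complete data. Section 5.5 allows day-30 and day-90 calls after an incomplete day-7 response, so the respondents may also differ between day 7 and day 90.

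**Step 2. Is there a stated allowance for non-response?** The pooled two-proportion formula for 65% versus 80% gives 138 per arm (151 with continuity correction), not 186. An allowance of about 25% would come close (138/0.75 = 184), but none is stated. If 75% of 186 respond (about 140 per arm), power is still about 81%. The main risk is therefore bias, not loss of power.

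**Step 3. Bias with no true effect.** Let true adherence be 65% in both arms, response be r, and adherence among non-responders be q. Adherence among respondents is (0.65 - (1 - r) x q) / r.

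With q = 40%:

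- r = 75%: (0.65 - 0.25 x 0.40)/0.75 = 73.3%
- r = 85%: (0.65 - 0.15 x 0.40)/0.85 = 69.4%; spurious difference 3.9 points
- r = 70%: (0.65 - 0.30 x 0.40)/0.70 = 75.7%
- r = 90%: (0.65 - 0.10 x 0.40)/0.90 = 67.8%; spurious difference 7.9 points
- r = 80% in both arms: (0.65 - 0.20 x 0.40)/0.80 = 71.25% in each; difference 0

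The result depends on q:

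- q = 50%: 70.0% versus 67.6% (2.4 points) for 75% versus 85% response, and 71.4% versus 66.7% (4.8 points before rounding) for 70% versus 90%.
- q = 65%: no bias at any response rate.

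Whenever q is below 65%, the arm with the higher response looks worse.

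**Step 4. A second pattern.** Suppose 80% of everyone responds, except that intervention-arm non-adherers respond at 60%. Intervention respondents then show 0.65 x 0.80 / (0.65 x 0.80 + 0.35 x 0.60) = 0.52/0.73 = 71.2%, against 65.0% in control. That is 6.2 points with no true effect, and with 186 assigned per arm the nominal 5% test rejects about 20% of the time. The mirror pattern in the control arm gives -6.2 points.

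**Step 5. Worst-case bounds for all assigned.** With response r in both arms and observed difference d, the bounds are r x d ± (1 - r) x scale range.

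- MMAS-4, d = 15 points, r = 80%: 12 ± 20, or -8 to +32 points
- MMAS-4, r = 90%: 13.5 ± 10, or +3.5 to +23.5 points
- MMAS-4, r = 70%: 10.5 ± 30, or -19.5 to +40.5 points
- SPER, d = 0.3 (assumed observed), r = 80%, range 10: 0.24 ± 2.0, or -1.76 to +2.24

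**The case against.** The strongest reply is that the sentence in 7.5 itself names telephone data as the source, and that beside an as-treated analysis the term may only mean analysing patients in their assigned arm. On that reading the fault is mostly one of wording. This stands in part, but the sentence also claims the entire assigned population, which the consent rules rule out.

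A reader might infer that the trial has no protection at all. The documents do not support that. The comparison is not disclosed at admission, interviewers are blinded, caregivers may answer, calls continue after an incomplete day-7 response, and patients who leave against medical advice are still called. Decliners may permit chart review, and completion is recorded for each subject (6.5). These measures limit assessment bias and missed contacts. They do not correct for selective agreement, and chart-only consenters still lack both primary endpoints.

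A reader might also want to redefine the arms strictly by admission day, or replace the as-treated analysis with a complier-average estimate. Neither follows. Section 5.2 assigns even-day patients to routine care when the nurse's caseload is full, so an admission-day rule would move them to the other arm. A complier-average estimate among respondents carries the same selection. Section 7.5 does not present the as-treated analysis as a check on non-response; the point is only that it cannot serve as one.

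Finally, 7.3 calls this a pilot and 12.1 says it is unfunded. That argues for a light remedy, not for keeping the label.

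**Conclusion.** The point holds as a mismatch between label and data, with no analysis to show how much it matters. Following the protocol yields a comparison of respondents by assigned arm, not an analysis of everyone assigned. This rests on the text alone.

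The size rests on assumptions. With non-responders at 40% adherence, the two response gaps shown produce 3.9 and 7.9 points, the larger being about half the 15-point target. With equal selection the bias is zero. At 80% response, an observed 15-point gain would not exclude a loss across all assigned patients in the worst case.

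A reader might infer that the bias would favour the attending nurse. The documents do not support a direction: if the relationship raises response and non-responders are less adherent, the bias runs against the nurse. Nor do they show that response will in fact differ.

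**What to change.** 1. **Relabel in 7.5.** Name the primary set *all assigned patients who are reached and consent, analysed in the arm assigned under the protocol*, and do not describe it as covering all assigned patients.
2. **Keep and report de-identified counts by assigned arm:** assigned, known died, unreached, declined, removed and surveyed, at day 7 and day 90. Case numbers are issued at enrolment (5.4) and completion is recorded (6.5), so a tally should be possible without individual data from non-consenters. Deaths among unreached patients may be undercounted, hence *known* died.
3. **Compare response between arms.**
4. **Add one tipping-point analysis per primary endpoint, using those counts.** For MMAS-4, vary assumed adherence among unsurveyed patients separately by arm until the conclusion changes. For SPER, do the same with their assumed mean score.

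Imputation for consenters who miss day 90 is optional; it does not address selection at consent. The consent model need not change.

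The cost is revised wording, a running tally and modest extra analysis, plus a label less favourable than intention to treat.
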